5.5 STRATEGIES FOR RECRUITMENT AND RETENTION

Recruitment and Consent procedures:

The dialysis care provider who has been selected by the clinic as one responsible for SPIRIT delivery at each clinic (so-called, "SPIRIT clinician champion") in both groups will generate a list of patients each quarter who meet the inclusion criteria. **Depending on the clinic's structure and workflow, the care provider who determines patients meeting these criteria may not be the same care provider, i.e., SPIRIT clinician champion who is responsible for SPIRIT delivery.**

From this list, the care provider will then assess the patient's willingness to meet with a recruiter from the research team. The recruiter will then approach willing patients during their scheduled dialysis clinic appointment to explain the study purposes and procedures. In a private room, written consent will be obtained from the

patient after the study is reviewed and understanding is established. The recruiter will then provide the patient with a study brochure and encourage him/her to talk to the surrogate regarding the study within the next 2-3 days (to avoid a cold call). Several days later, the recruiter will telephone the surrogate to assess his/her willingness to participate. **Using a Surrogate Verbal Consent script and form, the site coordinator will document time and date. Upon this verbal consent, the research staff at the Emory Study Coordination Center will conduct baseline data by phone.** For surrogates in the SPIRIT implementation clinics, the recruiter (at each study site) will schedule the first SPIRIT session to take place at the clinic 2 weeks hence, as is possible.

Recruitment will occur over 24 months beginning at the end of Year 1. We are highly experienced in recruiting seriously ill ESRD patients and their surrogates for research. Consent rates in our previous studies have been consistent at approximately 84% despite the studies' focus on end-of-life, the requirement that both patient and surrogate participate, and long-term follow-up. We expect a similar if not higher consent rate because the study involves a shorter follow-up time and minimal data collection directly from patients and surrogates. Based on our previous studies,¹⁸⁻²⁰ we conservatively anticipate that 427 patients (20%) will be *eligible and willing* to participate. To reach 400 dyads, we expect to enroll 21-22 dyads per cluster on average. These clinics each accept 10-70 new patients each year (total 700 additional patients), and thus our recruitment goal is readily achievable.

To Maximize Participant Retention, strategies found effective in retaining dyads over 12 months (dropouts, 3.8%) in our efficacy trial²⁰ will be used: we will

- a) obtain two backup contacts from each member of the dyad in the event that we cannot reach them by telephone and mail
- b) make confirmation phone calls 2 days prior to each follow-up
- c) make monthly check-in calls
- d) send holiday cards
- e) assign the same data collector whenever possible
- f) compensate each member of the dyad with gift cards (\$15 at baseline, \$15 at 2 weeks for the preparedness outcome assessment; \$20 at 3 months for the post-bereavement outcome assessment). Consistent with a pragmatic trial, participants will not be compensated for participating in the intervention. The Emory Study Coordination Center will be responsible for disbursement.

For Supplement Aims:

Participants will be recruited from the Emory dialysis centers and the UVA dialysis centers. First, patients who have been diagnosed with an early stage of dementia (mild to moderate) or are suspected of having cognitive impairment by a care provider will be referred by the dialysis APRN. The medical records of those patients will be reviewed to preliminarily determine eligibility by a research staff member. During the patient's dialysis treatment session at the center, the patient's care provider will gain permission for the staff member to explain the study. With the patient's permission, the staff member will approach the patient, briefly explain the study, obtain verbal consent to conduct the MOCA or SLUMS and UBACC screening. If the patient has met the criteria for both early stages of cognitive impairment and decision-making capacity, the research staff member will provide detailed study information and confirm his/her surrogate decision-maker. Written consent will then be obtained from the patient. The research staff member will obtain the name and phone number of the surrogate (or confirm with the medical record as necessary) and call the surrogate in 2-3 days to assess the surrogate's willingness to participate. Verbal consent will be obtained from the surrogate. At the time of surrogate consent, the staff member will schedule a telephone-based data collection session for baseline assessment in about 2 weeks.

To minimize in-person contacts, we will screen patients remotely/via phone whenever possible. Patients who are deemed eligible will be approached by a social worker during their dialysis treatment session or by phone to ask them about their willingness to be contacted via telephone by Emory research staff. Patients who agree to be contacted, a research staff member will call the patient, briefly explain the study, obtain verbal consent to conduct the cognitive screening using the MoCA and UBACC. Verbal consent will then be obtained from the

patient if screening occurred over the phone. The research staff member will obtain the name and phone number of the surrogate (or confirm with the medical record as necessary) and call the surrogate in 2-3 days to assess the surrogate's willingness to participate. Verbal consent will be obtained from the surrogate. At the time of surrogate consent, the staff member will schedule a telephone-based data collection session for baseline assessment in about 2 weeks.

For supplement cohort study:

At the next monthly check in phone call (as part of the parent study protocol), the research staff member will proceed with the procedures for the parent study and then introduce the participant to the supplement study, including the purpose and procedures and obtain verbal consent. After both members of the dyad have consented, the recruiter will schedule two data collection calls (T3 within 1 week and T4 at 6 months). If additional subjects are needed, we will contact those who already completed the study before the pandemic.

To Maximize Participant Retention, we will

- a) obtain two backup contacts from each member of the dyad in the event that we cannot reach them by telephone and mail
- b) make confirmation phone calls 2 days prior to the baseline and/or the SPIRIT session (intervention group)
- c) make scripted monthly check-in calls
- d) send holiday cards
- e) assign the same data collector whenever possible
- f) provide transportation support (\$20) for the SPIRIT session in person at the center (intervention group)
- g) compensate each member of the dyad with gift cards (\$20 at baseline; \$25 at post-intervention follow-up; and surrogates who complete post-bereavement assessment will receive \$30 at 1 month after the patient's death).

For supplement cohort study, each member of the dyad will receive an additional \$20 at the completion of T3 and \$30 at T4.

Recruitment of Care Providers for Implementation data collection, we will obtain a list of dialysis care providers from each dialysis center, who are willing to be contacted by the study staff for participating in implementation related data collection. This data collection is to obtain inputs from the care providers regarding SPIRIT implementation as part of routine dialysis care. Research study staff at the study site will contact care providers on the list using their preferred contact numbers or emails. Verbal Care Provider Informed Consent will be used in consenting process. Survey/Interviews will be scheduled to be conducted over the phone or in person at the convenience of the Care Provider. There will be no compensation for care provider's participation.

6 STUDY INTERVENTION(S)

6.1 STUDY INTERVENTION(S) ADMINISTRATION

6.1.1 STUDY INTERVENTION DESCRIPTION

SPIRIT Intervention:

All care providers responsible for SPIRIT delivery will follow the structured SPIRIT Interview Guide. All sessions will be conducted in a private room in the clinic. The goals of SPIRIT are to assist patients clarify their end-of-life preferences and to help surrogates understand the patient's wishes and prepare for the surrogate role. SPIRIT has two face-to-face sessions with patient and surrogate together. These sessions may occur using teleconferencing

software (Zoom) when surrogate decision makers live or work outside a 50-mile radius of patient's clinic. We project the monthly caseload for SPIRIT delivery will be 1-2 dyads per cluster on average.

During the first session (~45 min.), the care provider will assess the patient's and surrogate's cognitive, emotional, and spiritual/religious representations of the patient's illness, prognosis, and end-of-life care. This will allow the care provider to provide individualized information about topics, such as the effectiveness of life-sustaining treatment for people with end-organ failure, and assist the patient to examine his/her values about life-sustaining treatment at the end of life. The care provider will help the surrogate prepare for end-of-life decision-making and for the emotional burden of decision-making by actively involving the surrogate in the discussion. If the surrogate is someone out of the order of the hierarchical compensatory model⁷¹ (e.g., a sibling is chosen instead of a spouse), the care provider will explore potential family conflicts and encourage the dyad to talk with other family members and complete a healthcare power of attorney. A Goals-of-Care document will be completed at the end of the session to indicate the patient's preferences.

A brief second session (~15 min.) will be delivered about **approximately 2 weeks later, if possible. For PD patients who scheduled dialysis is varying, the second session of the SPIRIT Intervention can be scheduled to occur approximately 2-4 weeks hence, if possible.** This session is a follow-up to address remaining or new concerns and questions raised after the first session. The patient's Goals-of-Care document will be reviewed and assessed for the need for clarification or correction. The provider will document the patient's end-of-life preferences and the surrogate's name and relationship to the patient in the medical record. If the patient desires a DNR order, POLST, or MOST, the care provider will discuss with the patient's nephrologist and arrange a meeting to complete a treatment order form. We will track completion of these forms.

For Supplement Aims: the SPIRIT intervention will include one session only due to the patient's limited or absent short-term memory. During the COVID-19 pandemic, all SPIRIT sessions will be done via zoom whenever possible.

Usual Care

As required by CMS,⁵¹ written information on ADs is provided to a patient on the first day of dialysis, and a social worker reviews this information with patients and encourages them to complete an AD. This typically takes about 10 minutes. If completed, the presence of an AD is documented on the Plan of Care form. If a patient expresses a desire not to be resuscitated in the dialysis unit, a DNR order is written by a nephrologist and placed in the clinic record. If there is no DNR order in the record, a full code is presumed. A social worker or charge nurse reviews code status and updates it annually. Currently, all four states endorse the physician orders for life-sustaining treatment (POLST) paradigm; NM MOST (medical orders for scope of treatment), NC MOST, PA POLST, VA POST and GA POLST; these forms may be completed to complement ADs. None of the clinics employ routine identification of patients at high risk for death or structured ACP sessions targeting those patients.

6.1.2 DOSING AND ADMINISTRATION

Described above (6.1.1).

6.2 PREPARATION/HANDLING/STORAGE/ACCOUNTABILITY

6.2.1 INTERVENTIONIST TRAINING AND ACCOUNTABILITY

Care Provider Training for SPIRIT

The ideal individual to conduct ACP discussions is still unknown, but we believe it is not the profession per se but rather the willingness and appropriate training that make an individual suitable for conducting the discussions. Each dialysis clinic has identified a care provider designated to conduct SPIRIT sessions (e.g., ANP, RN, MSW). SPIRIT training will occur shortly after randomization for the initial implementation clinics and in early Year 4 for

the delayed implementation clinics. The SPIRIT trainers, trained and certified by the PI at the Study Coordination Center (at Emory), will conduct SPIRIT training for all four sites based on the manualized curriculum.

Care provider training will consist of a 1½-day, competency based program that has been used in our previous trials:

- Module 1 (1/2 day) to ensure understanding of end-of-life care issues and communication as key to improving end-of-life care and the Representational Approach (theoretical underpinnings of SPIRIT);
- Module 2 (1/2 day), as skill-base session to gain understanding of the SPIRIT intervention and delivery, including role plays. A 2-week practice period will be scheduled for integration of skills and exploration of additional learning needs; and
- Module 3 (1/2 day) for skill-demonstration and certification. These training sessions will be conducted in collaboration with the Emory Nursing Professional Development Center.

For Supplement Aims:

An RN who has been trained and certified for SPIRIT-dementia will deliver the intervention, who is currently working as the interventionist for the SPIRIT-AD study (IRB #00099738). SPIRIT sessions will be conducted in a private room at the dialysis center or virtually with ZOOM. At the beginning, the interventionist will administer the MoCA or SLUMS (depending on which test was used at enrollment), which should take about 10 minutes. The interventionist will begin the SPIRIT session by assessing the patient's and surrogate's cognitive, emotional, and spiritual/religious representations of the patient's illness, prognosis, and end-of-life care. This will allow the interventionist to provide individualized information about topics, such as the effectiveness of life-sustaining treatment for people with end-organ failure, and assist the patient to examine his/her values about life-sustaining treatment at the end of life. The interventionist will help the surrogate prepare for end-of-life decision-making and for the emotional burden of decision-making by actively involving the surrogate in the discussion. If the surrogate is someone out of the order of the hierarchical compensatory model⁵⁹ (e.g., a sibling is chosen instead of a spouse), the care provider will explore potential family conflicts and encourage the dyad to talk with other family members and complete a healthcare power of attorney. A Goals-of-Care document will be completed at the end of the session to indicate the patient's preferences. The delivery of SPIRIT-dementia incorporates so-called "enhanced consent techniques," such as reducing information load by proceeding in manageable segments or chunks, offering repetition of material, opportunity for rehearsal, and using targeted questioning to verify adequate comprehension prior to eliciting preferences for goals of care.⁶⁰⁻⁶² All sessions will be audio-recorded and transcribed. At the end of the session, the dyad will receive \$20 to compensate travel costs. The interventionist will schedule a follow-up call for the outcome assessment in the next 2-3 days.

6.2.2 FORMULATION, APPEARANCE, PACKAGING, AND LABELING

Not applicable.

6.2.3 PRODUCT STORAGE AND STABILITY

Not applicable.

6.2.4 PREPARATION

Not applicable.

6.3 MEASURES TO MINIMIZE BIAS: RANDOMIZATION AND BLINDING

Clinics covered by the same care provider who will deliver SPIRIT sessions will be combined to one cluster to avoid risk of contamination; this results in clusters (4 in GA, 3 in NC, 8 in NM, 5 in PA and 8 in VA). Because the numbers of available patients substantially vary across the clusters, to minimize group imbalance clusters will be stratified to three sizes: small (patient census ≤ 52), medium (53-105), and large (≥ 106). We will randomize clusters to either SPIRIT or usual care plus delayed SPIRIT, with randomly permuted blocks (sizes of 2 and 4) within cluster size stratum nested in each state, using a pseudo-random-number generator, by the Study Coordination Center.

Before the study starts, the Study Coordination Center will inform the group assignment for each cluster to the site PIs, with a unique ID consisting of abbreviations for state and cluster size stratum. While the heterogeneity in minority race/ethnicity across clusters improves the study's generalizability, stratification or pairing clusters by race/ethnicity is not feasible because some clinics uniquely serve one race with no comparable clinics within state. Group imbalances on race/ethnicity and other potential confounding factors will be examined and adjusted for in the analyses. The cluster randomized design prevents blinding patient-surrogate dyads and dialysis care providers to group allocation. However, research staff assessing effectiveness outcomes will be blind to group assignment.

For Supplement Aims:

[name] (biostatistician/Co-I) will generate a randomization scheme using stratified (by race), permuted block randomization with block size 5, using a random-number generator. Dyads will be randomized with equal allocation (1:1) to SPIRIT or usual care. Due to the nature of the intervention, blinding dyads to their group allocation is impossible, but the research staff assessing outcomes will be blind. Immediately after the completion of the baseline assessment by phone, the data collector will open a sealed envelope to identify group assignment and schedule an intervention session to take place ~ 2 weeks hence for SPIRIT as well as a follow-up data collection session in the next 2-3 days.

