9.2 SAMPLE SIZE DETERMINATION

We have an adequate sample size to detect clinically meaningful differences between SPIRIT and usual care for our primary outcomes. Statistical power is based on a random effects models: a generalized linear mixed model for binary outcomes (e.g., dyad congruence) and a linear mixed model for continuous outcomes (e.g., patient decisional conflict).

We conducted a simulation study to estimate power with 2-sided significance level alpha=.05, corrected for anticipated dropout and potential intraclass correlations (ICCs) ranging .01-.04, based on ICCs observed in our prior work. To estimate the power more conservatively, we used the effect sizes observed at 2 months²⁰ rather than those at 2 weeks,¹⁸ which are larger (e.g., for the composite outcome, *OR*=1.8 at 2 months, *OR*=4.4 at 2 weeks). The overall power to detect clinically meaningful differences is excellent for the primary outcomes and good for the post-death outcomes.

Power for comparing SPIRIT and usual care with 19 clusters				
Aim 1	Percent or min. difference	OR or variance	ICC ^a	Estimated power
Dyad congruence	48%	OR =2.0	0.02 0.04	0.92 0.84
Patient DCS	d =0.24	0.23	0.01 0.10	0.98 0.81
Surrogate DMC	d =0.22	0.20	0.01 0.10	0.99 0.80
Composite outcome	47%	OR =2.0	0.02	0.93
Aim 3				
Anxiety	d =1.35	7.0	0.01 0.03	0.84 0.80
Depression	d =1.60	10.0	0.01 0.03	0.85 0.79
PTSS-10	d =4.75	90.0	0.01 0.03	0.85 0.78

^a observed ICCs in our prior work; *d*=1/2 *SD*.

DCS, decisional conflict scale; DMC, decision-making confidence.

For Supplement Aims:

Because this is a pilot study, prior estimates of effect sizes were not available; thus a traditional sample size calculation was not performed. Instead we focused on calculating the minimum effect size that can be detected with adequate power (>=80%). Based on preliminary calculations, we found that a sample size of 30 will achieve 80% power to detect an effect size (Cohen's *f*²) of 0.28 (moderate-high), attributable to the treatment group indicator using an F-test at a 5% significance level. We will use the estimates of effect sizes obtained from this study for sample size calculations in future larger studies.

Supplement cohort study:

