9.4.2 ANALYSIS OF THE PRIMARY ENDPOINT(S)

SPIRIT effectiveness on the preparedness outcomes: Dyad congruence and the composite outcome (binary variables) will be analyzed by fitting a generalized mixed effects model for each, where the binary outcome is modeled in terms of a logit link⁹⁰ with both a random intercept and random slope to control for variation within and between subjects and clusters. The model also includes the intervention SPIRIT, cluster size and their interaction. For patient DCS and surrogate DMC scores, we will replace the logit link by the identity link with an additional error term. These models will allow us to examine whether SPIRIT was superior to usual care in the primary outcomes at 2 weeks and whether the effect of SPIRIT varies by cluster size. The analysis will be adjusted for potential covariates, such as race/ethnicity, and rural-urban status, in the model, including interaction between treatment and race/ethnicity.

For Supplement Aims:

To account for small sample size, resampling methods will be used for all analyses and 95% bootstrap confidence intervals of the differences in outcome scores will be reported.

- 1) Aim 1. SPIRIT effects on the preparedness outcomes:** For testing the effect of the intervention on dyad congruence, a paired binary outcome (congruent or not congruent), McNemar's test will be used. In addition, a logistic regression model will be used to test for differences in post-intervention outcomes by groups after adjusting for potential covariates. The adjusted ratio of odds of congruence in the intervention group versus the control group will be evaluated and reported as an effect size estimate.
- 2) Aim 1. SPIRIT effects on care decisions:** Differences in proportion of decisions made (e.g. stopping dialysis, DNR order, and hospice enrollment etc.) at 6-month follow up or death of patient will be described across groups and used as effect size. We will also explore time to event analysis to assess the difference in rate of risks between the two groups using non-parametric and semiparametric methods.
- 3) Aim 2. Surrogate post-bereavement distress (HADS scores):** Differences in the HADS subscale scores between the intervention and control groups will be assed using t-tests. Because, we estimate a 50% rate of death during the study, the number for this analysis would be n=15. A standardized difference between groups will be used as an effect size estimate.

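### State is a randomisation factor over thin strata, but the primary model does not prespecify it

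*Combined protocol and SAP*

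**What the plan says.** Section 6.3 merges clinics that share a SPIRIT provider and gives the count by state: "this results in clusters (4 in GA, 3 in NC, 8 in NM, 5 in PA and 8 in VA". Size classes are then set: "clusters will be stratified to three sizes: small (patient census ≤ 52), medium (53-105), and large (≥ 106". Assignment is by computer, "with randomly permuted blocks (sizes of 2 and 4) within cluster size stratum nested in each state". No further constraint on balance, overall or within state, is described, and the rule for choosing between the two block sizes is not given. On imbalance, 6.3 says: "Group imbalances on race/ethnicity and other potential confounding factors will be examined and adjusted for in the analyses".

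Section 9.4.2 gives the fixed part of the primary model: "The model also includes the intervention SPIRIT, cluster size and their interaction". The random part comes "with both a random intercept and random slope to control for variation within and between subjects and clusters". On covariates it says: "The analysis will be adjusted for potential covariates, such as race/ethnicity, and rural-urban status, in the model". State appears in none of these. Sections 9.4.3 and 9.4.9 carry the same approach over to the bereavement outcomes (Aim 3) and treatment intensity (Aim 4).

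**The concern.** Permuted blocks balance the arms only when blocks are filled. With so few clusters per stratum, many blocks are left part-used. A lone cluster is a coin toss, and two clusters drawn from a block of four can both go to the same arm. Stratifying on state and size together can therefore leave the arms uneven in both cluster count and state mix.

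The usual protection is to analyse by the factors used to randomise. Here one of the two factors, size, is in the model and the other, state, is not named. State could matter in this trial. The amendment history adds the Virginia site in January 2019, after the December 2018 deletion of the surprise-question criterion. Virginia's eight clusters therefore enrol under the broader rule throughout, while earlier sites recruited under both. If states differ on the outcome, any state imbalance that is drawn moves the SPIRIT estimate in that draw, and the unmodelled variation widens its interval.

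**Working it through.** **Inputs.** From 6.3: clusters per state GA 4, NC 3, NM 8, PA 5, VA 8; three sizes; blocks of 2 and 4. From 9.2: "We conducted a simulation study to estimate power with 2-sided significance level alpha=.05", 19 clusters, and for patient decisional conflict (DCS) difference 0.24 and variance 0.23. From 5.5: 400 dyads. Not in the documents, so assumed: the spread of clusters over sizes, the block-size rule, and the share of variance between states.

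**The plan's own power.** For the continuous outcomes, m = 400/19 = 21.05 dyads per cluster, design effect DE = 1 + (m - 1) x ICC, effective n per arm = 200/DE.

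| Outcome | ICC | DE | Recomputed | Section 9.2 |
|---|---|---|---|---|
| DCS | 0.01 | 1.20 | 0.995 | 0.98 |
| DCS | 0.10 | 3.01 | 0.823 | 0.81 |
| Surrogate confidence (0.22, variance 0.20) | 0.01 | 1.20 | 0.994 | 0.99 |
| Surrogate confidence | 0.10 | 3.01 | 0.810 | 0.80 |

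These agree to within 2 points. The plan prints no figure for strata or allocation balance.

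**Stratum size.** 4 + 3 + 8 + 5 + 8 = 28 clusters; 5 x 3 = 15 possible strata; 28/15 = 1.87 per stratum (NC 1.00, GA 1.33, PA 1.67, NM and VA 2.67). Two clusters drawn from a block of four share an arm with probability 1/3. If the two block sizes are equally likely, this is 1/2 x 1/3 = 1/6.

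**Allocation balance.** Simulated allocations, each cluster equally likely to be small, medium or large, 28 clusters:

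| Block rule (both fit the text) | Difference of 4 or more | 6 or more | A state in one arm |
|---|---|---|---|
| 2 or 4 drawn at random | 35% | 12% | 13% |
| 4 used only where at least 4 clusters remain | 26% | 6% | 6% |

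The one-arm state is nearly always NC; without NC, the 13% falls to about 2%. Under the second rule it can only be NC, and the value is exact. Its three clusters must fall in three different sizes (6/27) and then agree (1/4): 6/27 x 1/4 = 5.6%. An even spread over sizes, with block sizes drawn at random, gives 41%, 17% and 29%. With 20 clusters (no NM) and a random size mix, a difference of 4 or more occurs in 21-29% of draws.

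**Cost of unequal counts.** Relative efficiency is 4ab/(a + b)^2: 16:12 gives 768/784 = 0.980, and 18:10 gives 720/784 = 0.918. DCS power at ICC 0.10 with m = 400/28 is 0.906 at 14:14, 0.901 at 16:12 and 0.882 at 18:10.

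**Effect of a state term.** Cluster-mean simulation, 28 clusters, DCS values, assumed ICC 0.05. SD is the empirical SD of the estimate with no true effect.

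| State share of variance | Type I error without / with state | Power without / with | SD without / with |
|---|---|---|---|
| 0 | 0.050 / 0.048 | 0.96 / 0.94 | 0.0631 / 0.0663 |
| 0.02 | 0.046 / 0.050 | 0.93 / 0.93 | 0.0647 / 0.0654 |
| 0.05 | 0.042 / 0.053 | 0.91 / 0.94 | 0.0678 / 0.0657 |
| 0.10 | 0.034 / 0.050 | 0.84 / 0.94 | 0.0729 / 0.0660 |

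With no state variance the term raises the SD by 0.0663/0.0631 - 1 = 5%. At a share of 0.10, leaving it out raises the SD by 0.0729/0.0660 - 1 = 10%. Break-even is near 0.02.

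**The case against.** The strongest reply is that the plan already covers this. Section 6.3 promises to examine and adjust for confounders beyond race/ethnicity, and the 9.4.2 covariate list is open. A reader might infer that state is excluded from the analysis. It is not; it is only unnamed. That stands, but a general promise to adjust for imbalances once examined does not prespecify a factor known from the design.

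Second, a reader might infer that the scheme fails its own purpose. Section 6.3 ties the size strata to the varying numbers of available patients. Balance in patient numbers cannot be computed, because census by cluster is not given. Counting clusters does not show that failure.

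Third, a reader might infer bias or a raised false-positive rate. Allocation is random, and without state the simulated type I error is 0.034-0.050, nominal to conservative.

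Fourth, the gain depends on assumed state shares of 0.05-0.10, above the 0.01-0.04 ICC range in the text of 9.2, although its table runs to 0.10 for the two continuous outcomes. At smaller shares the term gains nothing. This stands as a limit on the size of the point. Evidence that states differ is also partial: the Synopsis does not map dialysis owners to states, and race mix is already a named covariate.

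**Conclusion.** The point holds as a modest gap in prespecification. The strata average about 1.9 clusters, so noticeable chance imbalance in cluster count is common (a difference of four or more in about 26-35% of draws). A state wholly in one arm is less common (about 6-13%, nearly always NC). These figures rest on the equal-size assumption and span the two block rules. Unequal counts by themselves matter little, at most about 2 power points. The remaining cost is chance confounding of arm with state in the realised allocation, and precision lost if states differ: nothing at a 0.02 share, and about 10 power points at 0.10 with ICC 0.05.

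The conclusion does not depend on which cluster count is right. Section 6.3 lists five states and 28 clusters, sections 3 and 4.1 say four states, the Synopsis site list omits NM, and 9.2 uses 19 clusters.

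A reader might also conclude that allocation should be redone. The documents do not support that: 6.3 releases assignments before the study starts, and no cluster is shown as awaiting randomisation.

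**What to change.** In 9.4.2, state that the Aim 1 models for congruence, decisional conflict, surrogate confidence and the composite include state as a fixed effect beside the size stratum. Fix this before any outcome is analysed by arm.

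Cost: one line of text and no change at sites. It takes four degrees of freedom with five states, or three with four, among 20-28 clusters. It costs about 2 power points (0.96 to 0.94 in the simulation) if states do not differ.

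Because 9.4.3 and 9.4.9 reuse the primary approach, add that the state term does not carry over automatically to Aims 3 and 4. Only patients who die contribute there. Section 4.1 anticipates about 80 deaths (8.1 says about 160), and amendment 7 reports under 4% of those recruited at that time. State terms on top of size, race/ethnicity and their interactions with arm could leave sparse or separated models. Use state adjustment there only as a sensitivity analysis where the data support it.

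Leave the allocation scheme as it is. Should any cluster remain unrandomised, allocate that batch in blocks of 2 within state, down a list ordered by patient census.
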